- The primary objective of this proposal is to generate new hypotheses and data for future studies by evaluating the effect of HIRREM as supplemental care for subjects with a number of neurological, cardiovascular, and psychophysiological diseases. The primary analytic outcome to determine the effect and feasibility of HIRREM is HRV as measured by standard outcomes collected using a BIOPAC device for continuous recording of heart rate and blood pressure. This also allows calculation of mean arterial pressure and baroreceptor sensitivity. We anticipate a decrease in sympathetic activity and an improvement in sympatho-vagal balance manifested as an increase in HRV parameters.
- Secondary objectives of this proposal include evaluation of the effects of HIRREM on:
 - Autonomic nervous system functions, as manifested by blood pressure and heart rate. Another expected result of a decrease in sympathetic activity and an improvement of sympatho-vagal balance may be a decrease in heart rate and blood pressure.
 - Psycho-physiological functional outcomes as measured using a standardized measure of health status the (EQ-5D), the Center for Epidemiologic Studies Depression Scale (CES-D), the GAD-7 measure of anxiety, the Insomnia Severity Index (ISI), and the PTSD Check List for civilians or military service members (PCL-C, or PCL-M, respectively). We expect to see an improvement in these measures following HIRREM.
 - Metrics for specific disorders will be measured according to relevant currently accepted assessment tools. Some of the conditions for which treatment is anticipated and the corresponding evaluation tools are in Appendix A. We expect to see improvement in these measures.

- Weight will be measured at the enrollment visit (V1), completion visit (V2) and follow-up visit (V3) to determine the potential impact of HIRREM on weight.
- Reaction time will be measured using the clinical reaction time enrollment visit (V1), completion visit (V2) and follow-up visit (V3).

Research Design and Methods:

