This protocol is an assessment of the functional and physiological effects of HIRREM on neurological, cardiovascular, and neurophysiological disorders. It will be a non-randomized, open label, and unblinded before-and-after trial. The intention of this protocol is to evaluate the effect of HIRREM on an objective, physiological common denominator (HRV), across a variety of relevant conditions, as well as changes in clinical symptoms scales, to generate hypotheses and pilot data for investigation in future proposals. HIRREM will be offered as deemed potentially advantageous by the investigator. Patients will be recruited to receive eight to twenty HIRREM sessions in addition to their usual care. HIRREM sessions will be completed over a one month period. Measurements for the primary and secondary outcomes will be obtained at the initial visit and after completion of HIRREM therapy. A follow-up visit (V3) will be performed four to eight weeks after the completion visit (V2). This will consist of several representative questionnaires and surveys and a repeat of recording of blood pressure and heart rate using the BIOPAC device.

1) Subjects Selection Criteria:

Male and Female adults and children over the age of 11 years with a clinical diagnosis consistent with the aims of this proposal, who also meet the inclusion criteria outlined below and are interested in receiving HIRREM, will be enrolled. Subjects will be recruited by physician referral, word of mouth, and through advertisement. Physicians who want to inform prospective subjects about the availability of the research will be provided with copies of the IRB approved consent form and IRB approved ad which they may give to prospective subjects. The physicians do not obtain subjects' consent for the research or act as representatives of the investigators. Physicians provide prospective subjects with information about contacting investigators for information or enrollment; and/or seek or obtain the prospective subjects' permission for investigators to contact them. The participant must be able to provide informed consent.

Inclusion Criteria:

- Male and female adults and children aged 11 years and older.
- Subjects who are over the age of 18 must be able to give informed consent. Children must be able to sign an assent form and have a signed parental permission form.

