Data will be analyzed using the most recent versions of SAS (SAS Institute, Inc., Cary, NC). Prior to performing analyses related to the hypotheses, histograms and descriptive statistics will be computed to examine the characteristics and distributions of the data. As detailed below, analytical methods will be conducted through generalized linear models that allow specification of appropriate distribution as well as various covariance types to ensure that inference tests can be interpreted conventionally. If required, nonparametric equivalents to the proposed methods will be used to analyze variables not well characterized by standard distributions. Unless otherwise stated, all relevant analyses will be two-tailed and $p < 0.05$ will be used to determine statistical significance. Because this proposal is designed to estimate effect sizes for future pilot and definitive trials, care will be taken to provide point estimates of effect size for each outcome along with corresponding 95% CI.

This primary objective of this protocol is to evaluate the effect of HIRREM in neurological, cardiovascular, and psychophysiological disorders as measured by standard HRV parameters. Also, a variety of secondary outcomes will assess the impact on functional and physiological measures (BP and HR), a number of standard disorder specific clinical measures, and subjective psychophysiological outcomes. The primary analysis will be examining group differences on the post-HIRREM measure while controlling for baseline levels (i.e., group treated as a fixed effect, with baseline scores entered as a covariate in a generalized model assuming a normal distribution and identity link). Changes in all secondary measures will be indexed using the GLM using the repeated measurements within each individual. The groups will be comprised of a collection of individuals from within the study with a common clinical disorder, although exploratory analysis will also evaluate for common effects in consecutively enrolled subjects.

Human Subjects Protection:

1) Consent and Assent

Written informed consent, or assent and parental permission will be obtained by the research staff from each competent subject.

2) Confidentiality and Privacy

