Appendix B: Medical History Form
 Medical History Form

First Name: _____

Date: _____

1. Please check whether you have the following medical problems/health history:

	Yes	No	Year of onset	If yes, please explain
High Blood Pressure				
Stroke				
Seizure/Epilepsy				
Heart Attack				
Heart Arrhythmia				
Lipid Disorder/High Cholesterol				
Diabetes				
Cancer				
Thyroid Disorder				
Fibromyalgia				
Other Chronic Pain				
Chronic Fatigue				
Headaches				
Migraines				
Tinnitus (ringing in the ears)				
Vertigo/Dizziness				
Stress/Anxiety Disorder				
Post-Traumatic Stress Disorder				
Depression				

Insomnia				
Hot Flashes				
ADD/ADHD				
Autism Spectrum Disorder/Asperger's				
Learning Disability/Dyslexia				
Impaired Memory/Mild Cognitive Impairment				
Sports-Related Concussion				
Traumatic Brain Injury/Head Injury				
Difficult Birth (Premature, Induced, C-Section, etc.)				
Other				
Any Surgery				

2. Please list your prescribed medications (those taken regularly and PRN/as-needed/rescue) and duration taking them (for how long, how many times per week/month, or last dose).

Medication	Dose	Time of day taken	Duration taking this

3. Please list any over the counter medication, supplements, vitamins, herbs, etc. that you take (those taken regularly and PRN/as-needed/rescue) and duration taking them (for how long, how many times per week/month, or last dose).

Name	Dose	Time of day taken	Duration taking this

Initial HIRREM Screening

Name: _____ Email address: _____
 Address: _____ Telephone number(s): _____
 Date of birth: _____ Gender: _____
 Referred by: _____ Date screened: _____

Primary complaint:

Secondary complaints:

Other medical problems:

Medications (prescriptions, PRN/as-needed/rescue medicines, over the counter, supplements, vitamins, herbs, etc.) and duration taking them (for how long, how many times per week/month, or last dose):

Comments:

Secondary HIRREM Screening

Name: _____

Date of birth: _____

Date screened: _____

Race: _____

Who is your primary care physician/contact number?

Do you see any other health care providers regularly or use any integrated/complimentary therapies (acupuncture, yoga, massage, healing touch, etc.)?

Please list an emergency contact, the relation, and a phone number.

General questions:

1. Do you consume alcohol? Yes No
 - a. If so, how much? _____
 - b. If so, how often? _____
 - c. If so, what type? _____
2. Do you consume caffeine (coffee, tea, energy drinks, chocolate, etc.)? Yes No

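### The primary between-disorder model adjusts only for one baseline HRV reading, so age- or sex-related HRV differences between groups are only partly removed and can appear as differences in response

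*Combined protocol and SAP*

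**What the plan says.** Under Research Design and Methods the design is stated plainly: "It will be a non-randomized, open label, and unblinded before-and-after trial". Eligibility under Subjects Selection Criteria covers "Male and female adults and children aged 11 years and older", with no upper age limit. Objectives and Hypotheses fixes the primary outcome: "The primary analytic outcome to determine the effect and feasibility of HIRREM is HRV".

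Section 6, Statistical Analysis, then says: "The primary analysis will be examining group differences on the post-HIRREM measure while controlling for baseline levels". The model has "group treated as a fixed effect, with baseline scores entered as a covariate in a generalized model assuming a normal distribution and identity link"; the phrase "with baseline scores entered as a covariate" is the only adjustment it names. On what a group is: "The groups will be comprised of a collection of individuals from within the study with a common clinical disorder". Secondary measures are handled differently, through repeated measurements on the same person.

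No section names age or sex as a covariate, stratum, matching factor or sensitivity analysis. The covariance types mentioned in section 6 are covariance structures, not covariates. Both variables are collected: the Initial HIRREM Screening form in Appendix B has "Date of birth: _____ Gender" fields.

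**The concern.** In a purely before-and-after analysis each person is their own control, and stable characteristics such as age and sex drop out of the change. The stated primary analysis is not of that kind. It is an analysis of covariance (ANCOVA) that contrasts diagnostic groups on the post-treatment value, and nothing in the design balances age or sex between those groups. The conditions named in the protocol include ADHD and dyslexia as well as hot flashes and mild cognitive impairment, so similar age and sex mixes cannot be taken for granted.

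Baseline adjustment would deal with this if the baseline reading captured each person's usual HRV without error. It is a single resting recording of at least 8 minutes. The completion reading follows about a month of sessions plus up to two weeks. If the two readings correlate imperfectly, part of any pre-existing group gap survives adjustment and looks like a difference in response.

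The estimates are the study's product. Section 6 promises effect sizes with 95% confidence intervals for later trials, and the introduction gives finding cohorts for further study as one goal.

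**Working it through.** The plan has no figure to reproduce: the target of 300 subjects comes without power, SD or group sizes. The check is of the mechanism.

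**Inputs from the documents.** Group as a fixed effect; baseline score as the only covariate; normal model with identity link; two-sided 5% test; no randomisation.

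**Inputs assumed.** HRV gap between two groups due to age or sex (in within-group SDs), test-retest correlation rho, and group size n. HIRREM has the same effect, or none, in both groups.

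**Bias.** Without a difference in response, both readings show the same group gap. The within-group slope of post on baseline is rho, so

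adjusted difference = gap - rho x gap = (1 - rho) x gap.

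- Low end: (1 - 0.8) x 0.5 = 0.10 SD.
- High end: (1 - 0.6) x 1.0 = 0.40 SD.
- Zero gap: 0.

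**False-positive rate.** The standard error of the group coefficient is approximately sqrt(1 - rho²) x sqrt(2/n) x sqrt(1 + gap²/4).

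- High end, n = 50: 0.8 x 0.2 x 1.118 = 0.179; 0.40/0.179 = 2.24, which gives rejection of about 61%.
- Low end, n = 30: 0.6 x 0.258 x 1.031 = 0.160; 0.10/0.160 = 0.63, which gives about 10%.

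Simulation (3,000 runs per setting) agrees: about 10% to 40% with 30 per group and 13% to 61% with 50 per group. With 10 per group, over the same ranges, it is about 7% to 16%.

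**Wider ranges.** Write the gap as r x D, where r is the age-HRV correlation within groups and D the age gap in within-group SDs of age. With r from 0.3 to 0.5, D from 1 to 2 and rho from 0.5 to 0.9, the bias runs from 0.3 x 1 x 0.1 = 0.03 SD to 0.5 x 2 x 0.5 = 0.50 SD. Simulated rejection rates (2,000 runs per setting):

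| Per group | Baseline only, full range | Mid case (r 0.3, D 2, rho 0.7; bias 0.18 SD) |
|---|---|---|
| 30 | 6% to 49% | 15% |
| 75 | 7.5% to 88% | 32% |
| 150 | 10% to 99% | 54% |

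With r = 0 the rate stays near 5%. With age in the model, and age the only cause of the gap, bias is within 0.011 SD and rejection 3.6% to 6.1%. Sex was not simulated; the same algebra applies to a sex imbalance.

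**When age is not the only cause.** Take rho = 0.7, r = 0.4 and, where there is an age gap, D = 1.25, so that the age-related gap is 0.4 x 1.25 = 0.5 SD. Given age, the test-retest correlation falls to (0.7 - 0.16)/(1 - 0.16) = 0.643. A disorder-related gap of 0.5 SD then leaves 0.5 x (1 - 0.643) = 0.18 SD after age adjustment.

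| Source of gap | Bias, baseline only | Bias, age added |
|---|---|---|
| Age only | 0.15 | 0.00 |
| Age and disorder, same direction | 0.30 | 0.18 |
| Age and disorder, opposite directions | 0.00 | -0.18 |
| Disorder only | 0.15 | 0.18 |

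With age added, rejection in the second row is still 12% (30 per group) or 19% (50 per group). In the third row it rises from about 5% to 12% or 17%.

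**The case against.** The strongest reply is that the driving premise lies outside the documents. They do not say that HRV depends on age or sex, and they give no age or sex mix for any disorder group. The range from 11 upward is study-level eligibility, not a description of any group. This stands: the size is conditional, and a gap of zero is not excluded.

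Second, adjustment is not a cure. The protocol's opening section links many of these conditions to low HRV, so gaps due to the disorder itself are at least as well supported as gaps due to age. The last table shows that adding age then leaves bias, and can create it where the two gaps had cancelled. This also stands, and it limits what the fix may claim. It does not justify leaving out an observed, routinely recorded difference between groups.

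Third, for pairs such as hot flashes against ADHD, the groups may barely overlap in age or sex. An age term would then extrapolate, and sex could be nearly collinear with group. That is a reason to check overlap first.

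Fourth, the study is hypothesis-generating, and earlier disorder subsets from it had 10 subjects, where the inflation of the error rate is modest. That lowers the stakes for the test. It does not affect the bias in the point estimate, which does not depend on group size.

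A reader might also infer that the plan will rank disorders by these contrasts. It does not say so; finding cohorts is given as one goal, without a stated rule.

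**Conclusion.** The point holds in a limited form. The primary model compares non-randomised diagnostic groups with only one imperfectly repeatable baseline reading as covariate, so an age- or sex-related HRV gap is only partly removed. The expected false difference is (1 - rho) x gap, or 0.10 to 0.40 SD if the gap is 0.5 to 1.0 SD and rho is 0.6 to 0.8. It is zero if age and sex are unrelated to HRV or balanced across groups. The gap, rho and group sizes are all assumptions.

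Three stronger readings are not supported:

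- That the contrasts will be biased by this amount. The documents give no figure that would show it.
- That adding age and sex restores an unbiased contrast and a 5% error rate. This holds only if they are the sole source of the gap.
- That the within-person secondary analyses share the flaw. They do not, unless they contrast disorder groups.

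Separately, every group receives HIRREM, so a difference between groups does not estimate HIRREM's effect, with or without these covariates. This is a worthwhile, inexpensive improvement rather than a fatal fault.

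**What to change.** In section 6:

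- Add age (continuous, with a quadratic term if residual plots call for it) and sex as fixed covariates next to the baseline score in the primary between-disorder model. Make the same change in a secondary model only where it contrasts disorder groups.
- Report the baseline-only model alongside.
- Show the age and sex distribution of each group, and omit the age or sex adjustment for contrasts in which the groups barely overlap on it.
- State that between-disorder contrasts are descriptive, because HRV differences due to the disorders themselves leave the same kind of residual bias and adjustment does not make the contrasts estimates of HIRREM's effect.
- Derive age into the analysis file before identifiers are destroyed as the Confidentiality and Privacy section foresees, in case date of birth is treated as one.

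The cost is a few sentences and two or three degrees of freedom, with no new data collection. The downside is that adjustment can increase bias where a disorder-related gap runs opposite to the age gap, which is why both models should be shown.

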Appendix A: Examples of Disease Specific Assessment Tools

Condition	Assessment Tool
Traumatic Brain Injury	Rivermead Post-Concussion Symptoms Questionnaire
Headache	Daily Headache Diary
Hot Flashes	Daily Diary for Hot Flashes
Mild Cognitive Impairment	Montreal Cognitive Assessment (MoCA)

Appendix B: Medical History Form
 Medical History Form

First Name: _____

Date: _____

1. Please check whether you have the following medical problems/health history:

	Yes	No	Year of onset	If yes, please explain
High Blood Pressure				
Stroke				
Seizure/Epilepsy				
Heart Attack				
Heart Arrhythmia				
Lipid Disorder/High Cholesterol				
Diabetes				
Cancer				
Thyroid Disorder				
Fibromyalgia				
Other Chronic Pain				
Chronic Fatigue				
Headaches				
Migraines				
Tinnitus (ringing in the ears)				
Vertigo/Dizziness				
Stress/Anxiety Disorder				
Post-Traumatic Stress Disorder				
Depression				

Insomnia				
Hot Flashes				
ADD/ADHD				
Autism Spectrum Disorder/Asperger's				
Learning Disability/Dyslexia				
Impaired Memory/Mild Cognitive Impairment				
Sports-Related Concussion				
Traumatic Brain Injury/Head Injury				
Difficult Birth (Premature, Induced, C-Section, etc.)				
Other				
Any Surgery				

2. Please list your prescribed medications (those taken regularly and PRN/as-needed/rescue) and duration taking them (for how long, how many times per week/month, or last dose).

Medication	Dose	Time of day taken	Duration taking this

3. Please list any over the counter medication, supplements, vitamins, herbs, etc. that you take (those taken regularly and PRN/as-needed/rescue) and duration taking them (for how long, how many times per week/month, or last dose).

Name	Dose	Time of day taken	Duration taking this

Initial HIRREM Screening

Name: _____ Email address: _____
 Address: _____ Telephone number(s): _____
 Date of birth: _____ Gender: _____
 Referred by: _____ Date screened: _____

Primary complaint:

Secondary complaints:

Other medical problems:

Medications (prescriptions, PRN/as-needed/rescue medicines, over the counter, supplements, vitamins, herbs, etc.) and duration taking them (for how long, how many times per week/month, or last dose):

Comments:

Secondary HIRREM Screening

Name: _____

Date of birth: _____

Date screened: _____

Race: _____

Who is your primary care physician/contact number?

Do you see any other health care providers regularly or use any integrated/complimentary therapies (acupuncture, yoga, massage, healing touch, etc.)?

Please list an emergency contact, the relation, and a phone number.

General questions:

1. Do you consume alcohol? Yes No
 - a. If so, how much? _____
 - b. If so, how often? _____
 - c. If so, what type? _____
2. Do you consume caffeine (coffee, tea, energy drinks, chocolate, etc.)? Yes No
 - a. If so, how much? _____
 - b. If so, how often? _____
 - c. If so, what type? _____
3. Are you a: Current smoker Ex-smoker Never smoked
 - a. If you have ever smoked, how much? _____
 - b. If you have ever smoked, how often? _____
 - c. If you have ever smoked, what type? _____
4. Do you have a history of addiction (substance abuse, shopping, etc.)? _____
5. Were you in the military? Yes No
 - a. If so, how many deployments/years did you serve? _____
6. Have you ever had any physical or emotional trauma (accidents, head injuries, childhood events, traumatic events, bad relationships, abuse)? Yes No
7. What is your marital status? Married Divorced Single
 Widowed Other
8. Do you have any children? Yes No
 - a. If so, how many and what age? _____
 - b. Have you ever lost a child? Yes No

Sleep

1. How do you usually sleep? _____

- a. Do you have any trouble falling asleep? Yes No
- b. Do you have any trouble staying asleep? Yes No
- c. Do you wake up rested? Yes No

Headaches/Migraines

- 1. Do you have headaches? Yes No
 - d. If so, how many per week/month? _____
 - e. If so, how long have you had them? _____
 - f. If so, do you do anything to alleviate them? _____
- 2. Did headaches occur from a concussion/TBI? Yes No
- 3. Do you have migraines? Yes No
 - a. If so, how many per week/month? _____
 - b. If so, how long have you had them? _____
 - c. If so, do you do anything to alleviate them? _____

Concussion/Traumatic brain injury (TBI)

- 1. Have you ever had any concussions or TBIs? Yes No
 - a. Was there more than one concussion or TBI? _____
 - b. If so, how many and what kind? _____
 - c. If so, when did it occur/what was the cause? _____
 - d. If so, did you lose consciousness? _____
 - e. If so, did you have to go to the hospital? _____
 - f. Were you hospitalized? If so, for how long? _____
 - g. Did the injury require brain surgery or drainage of blood or fluid from in or around the brain? _____
 - h. Have you ever had any other head injuries? _____

PTSD

- 1. Do you have post-traumatic stress disorder? Yes No
- 2. How long have you had PTSD symptoms? _____
- 3. Have you seen a physician for this? Yes No
- 4. Do you have a formal diagnosis of PTSD? Yes No
 - a. If so, when was the diagnosis made? _____
- 5. If you were in the military, in your opinion, did the traumatic event most responsible for your PTSD occur as part of your military service or did it occur as part of civilian life?
 - Military Civilian
 - a. If military, was it related to a blast injury? Yes No

ADHD

- 1. Do you have difficulty with focus and concentration? Yes No
- 2. How long have you had these symptoms? _____
- 3. Have you seen a physician for this? Yes No
 - a. Did you have a formal evaluation? Yes No
